6.2 SUMMARIES OF CONDUCT OF STUDY

Enrollment, patient disposition, and incidence of protocol deviations will be summarized descriptively for the ITT population.

6.3 SUMMARIES OF DEMOGRAPHIC AND BASELINE CHARACTERISTICS

Demographic and baseline characteristics (such as age, sex, race, disease severity, APOE4 status, and use and non-use of background therapy for AD) will be summarized descriptively for the ITT population.

Descriptive summaries of continuous data will present the mean, SD, median, minimum, and maximum. Descriptive summaries of discrete data will include frequencies expressed in terms of number and percentage of patients.

The primary and exploratory analyses will include all randomized patients, with patients grouped according to the treatment assigned at randomization until the OLE study.

6.4 SAFETY ANALYSES

The safety analysis population will include all patients who completed the DBTP and received at least one dose of study drug in either Study BN29552 or BN29553 and entered the OLE study. Patients will be grouped according to the treatment actually received until the first visit of the OLE study.

- Incidence, nature, and severity of adverse events
- Incidence, nature, and severity of serious adverse events
- Incidence of adverse events of special interest
- Incidence and nature of MRI safety findings: ARIA-E and ARIA-H
- Incidence of treatment discontinuations due to adverse events
- Mean changes in clinical laboratory tests from baseline over time, incidence of treatment-emergent abnormal laboratory values, and abnormal laboratory values reported as adverse events
- Mean change in ECG assessments from baseline over time and incidence of abnormal ECG assessments
- Incidence of immunogenicity as evidenced by antibodies to crenezumab or other components of drug product
- Mean change in vital signs (blood pressure, heart rate) from baseline over time and incidence of abnormal vital sign measurements
- Changes in CSSR-S scores from baseline over time.

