2. OBJECTIVES AND ENDPOINTS

This study will assess the long-term safety and tolerability of crenezumab administered to all patients who completed Studies BN29552 (CREAD) and BN29553 (CREAD2) and who meet the eligibility criteria for this OLE study. An exploratory objective of this OLE study is to investigate the effect of crenezumab on the underlying disease process and course. Specific objectives and corresponding endpoints for the study are outlined in [Table 1](#).

Table 1 Objectives and Corresponding Endpoints

Primary Safety Objective	Corresponding Endpoints
To assess the long-term safety and tolerability of crenezumab (60 mg/kg IV Q4W) in eligible patients with AD who participated in Study BN29552 or BN29553 and completed the Week 105 study visit	
 • Nature, frequency, severity, and timing of adverse events and serious adverse events • Vital signs, blood tests, ECGs, and C-SSRS • Adverse events of special interest, specifically pneumonia • Adverse events as assessed by MRI: ARIA-E and ARIA-H • The immunogenic potential of crenezumab through measurement of antibodies directed against crenezumab and other components of the drug product and assessment of their relationship with other outcome measures
Exploratory Efficacy Objectives	Corresponding Endpoints
To evaluate the long-term effect of crenezumab on global outcomes of disease progression	
 • Change from baseline during the OLE in CDR-SB
To evaluate the long-term effect of crenezumab on cognition	
 • Change from baseline during the OLE as measured by the ADAS-Cog-13 • Change from baseline during the OLE using the MMSE • Change from baseline during the OLE using ADAS-Cog-12
To evaluate the long-term effect of crenezumab on disease severity	
 • Change from baseline during the OLE using CDR-GS
To evaluate the long-term effect of crenezumab on patient dependence	
 • Change from baseline during the OLE using scores derived from the ADCS-ADL total scale
To evaluate the long-term effect of crenezumab on patient function	
 • Change from baseline during the OLE using the ADCS-ADL, the instrumental subscale, and/or the FAQ

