4.5.5.8 Columbia–Suicide Severity Rating Scale

The Columbia-Suicide Severity Rating Scale (C-SSRS; <http://www.cssrs.columbia.edu>) is an assessment tool used to assess any new instances of suicidality *since the last visit*. The structured interview prompts recollection of suicidal ideation, including the intensity of the ideation, behavior, and attempts with actual or potential lethality. *The* C-SSRS will be collected as indicated in the schedule of activities (see [Appendix 1](#)). The assessment will be completed by a certified C-SSRS rater after he or she interviews the patient and, *if necessary*, the patient's caregiver during the study visit.

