6.5 EFFICACY ANALYSES

All efficacy data during the open-label study will be summarized using descriptive statistics for the ITT population. Observed values and change from the OLE baseline values at each scheduled visit will be summarized.

For all continuous safety parameters, efficacy parameters, and biomarkers, *descriptive statistics for the change from baseline will be generated using the baseline value for the*

OLE study (defined as the last value recorded during the DBTP). *Descriptive statistics may also be generated for the change from the DBTP baseline.*

All efforts will be made to minimize missing data. Descriptive summaries of the number of patients with missing data and the timing and reasons for discontinuation from study will also be provided. Additional details will be documented in the SAP.

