	OLE Scr. ^b	Visit 1 OLE Wk 1 ^c	OLE Wk 5 and Every 4 Wks thereafter (± 7 days) ^c	Visit 4 OLE Wk 13 (± 7 days) ^{c,d}	OLE Wk 25 (± 7 days) ^{c,d}	OLE Wk 53 (± 7 days) ^{c,d}	OLE Wk 77 (± 7 days) ^{c,d}	OLE Wk 105 and Every 52 Wks thereafter (± 7 days) ^{c,d}	Last Dose in OLE +4 Wks (or ET)	Last Dose in OLE +16 Wks	Final Annual Visit for OLE Discon. before Wk 53/105 ^e	Last Dose in OLE +4 Wks	Last Dose in OLE +16 Wks
Concomitant medications		x	x	x	x	x	x	x	x	x	x	x	x
Adverse events		x	x	x	x	x	x	x	x	x	x ^u	x	x
Study drug administration ^c		x	x	x	x	x	x	x					

ADA=anti-drug antibody; ADAS-Cog13=Alzheimer's Disease Activity Scale Cognition 13; ADCS-ADL=Alzheimer's Disease Cooperative Study-Activities of Daily Living; CDR=Clinical Dementia Rating; CSF=cerebrospinal fluid; C-SSRS=Columbia Suicide Severity Rating Scale; DBTP=Double-Blind Treatment Period; *Discon.*=Discontinuation; eCRF=electronic Case Report Form; EQ-5D-5L= EuroQOL 5-Dimension, 5-Level questionnaire; ET=early termination; FAQ=Functional Activities Questionnaire; FCSRT-IR=Free and Cued Selective Reminding Test-Immediate Recall; MMSE=Mini Mental State Examination; MRI=magnetic resonance imaging; NPI-Q=Neuropsychiatric Inventory-Questionnaire; OLE=open-label extension; PD=pharmacodynamic; PET=positron emission tomography; PK=pharmacokinetic; Pts=patients; QOL-AD=Quality of Life-Alzheimer's Disease; *Scr.* =screening; SLV=since last visit; Wk=week; ZCI-AD=Zarit Caregiver Interview for Alzheimer's Disease.

Note: The visit window is ± 7 days for dosing days and ± 3 days for all other visits. For patients who terminate early, assessments listed in the visit "Last Dose in OLE +4 weeks [or ET visit]" should be completed.

^a Patients who continue treatment with crenezumab after completing of the study will not have any follow-up visits.

^b Assessments performed at Week 105 of the *parent studies* BN29552 and BN29553 will be used as screening assessments for the OLE study *as well as* an OLE protocol-specific pre-infusion coagulation assessment (*which can be done any time after consent*). If needed to complete assessments for OLE eligibility, an extra unscheduled visit can be done after *consent and before* Week 1, Visit 1 of the OLE.

Appendix 1

Schedule of Activities: Open-Label Extension Study (cont.)

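### C-SSRS is to be analysed only as change from baseline, although the form records what is new since the last visit, and no incidence summary is planned

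*Combined protocol and SAP*

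**What the plan says.** Section 2 (Table 1) lists "Vital signs, blood tests, ECGs, and C-SSRS" among the endpoints of the primary safety objective. Section 4.5.5.8 says that the C-SSRS "is an assessment tool used to assess any new instances of suicidality" arising after the preceding visit. Appendix 1 schedules the SLV form and explains the abbreviation as "SLV=since last visit". The form is marked at OLE Weeks 25, 53, 77 and 105, every 52 weeks after that, and 4 weeks after the last dose. It is not marked at OLE screening or Week 1.

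The planned analysis is the last bullet of Section 6.4, repeated in the synopsis under Primary Analysis: "Changes in CSSR-S scores from baseline over time". The other measurements in that list are treated more fully. For ECG, for example, the plan is "Mean change in ECG assessments from baseline over time and incidence of abnormal ECG assessments", and laboratory tests and vital signs follow the same pattern.

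On baseline, Section 3.2 takes the parent-study Week 105 data. Section 6.5, for continuous parameters, uses the baseline of the "OLE study (defined as the last value recorded during the DBTP", and also allows change from the double-blind baseline.

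**The concern.** A change score makes sense for a quantity with a running level, such as a QT interval or a blood pressure. A since-last-visit form has no such level, because each completed form reports what happened in its own window. Subtracting one report from another compares two windows and does not say whether something new happened in the later one.

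The safety question in an extension is how many patients report suicidal ideation or behaviour on open-label drug, and in how many it is new or worse. The bullet as written does not answer it. No C-SSRS score, category of ideation or behaviour, or treatment-emergent rule is defined anywhere in the documents supplied.

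**Working it through.** **1. The texts side by side**

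| Question | Source | Answer |
|---|---|---|
| Is it a primary safety endpoint? | Section 2, Table 1 | Yes |
| What does one form record? | Section 4.5.5.8; Appendix 1 | New instances since the last visit |
| What is analysed? | Section 6.4; synopsis | Change in score from baseline |
| Is an incidence planned? | Section 6.4 | For laboratory tests, ECG and vital signs, yes; for C-SSRS, no |
| What is baseline? | Sections 3.2 and 6.5 | Parent Week 105 data, or the last double-blind value |

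**2. One patient.** Change = score at OLE visit − score at baseline. If both equal s, with s above zero, the change is s − s = 0. Yet the OLE form with score s is itself the record of a new instance. This holds for any s and needs no assumed rate.

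**3. A group, if scores are averaged.** Mean change = (sum of visit scores − sum of baseline scores) / N. For N, the plan's own figure reproduces: 1500 × (1 − 0.35) × (1 − 0.05) = 926.25, stated as approximately 925. The documents give neither a suicidality rate nor a score, so the following are assumptions: every positive patient scores 2, and the patients positive at the visit are not those positive at baseline.

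| Positive at baseline | Newly positive at visit | Mean change | New reports |
|---|---|---|---|
| 1% (9) | 1% (9) | (9×2 − 9×2)/925 = 0.00 | 9 (1.0%) |
| 2% (18) | 2% (18) | (18×2 − 18×2)/925 = 0.00 | 18 (1.9%) |
| 5% (46) | 5% (46) | (46×2 − 46×2)/925 = 0.00 | 46 (5.0%) |
| 2% (18) | 4% (37) | (37×2 − 18×2)/925 = 0.04 | 37 (4.0%) |

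The zeros follow from assuming equal rates and severity at both times. The last row shows that even a doubling moves the mean by only 0.04 points.

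**4. A display by visit.** With 9 positive patients at each of Weeks 25, 53, 77 and 105, the number with any OLE report lies between 9 (the same patients each time) and 4 × 9 = 36 (all different, 36/925 = 3.9%). Visit-by-visit results alone cannot say which.

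**The case against.** The strongest reply is that averaging is not what the plan says. The laboratory, ECG and vital-sign bullets speak of mean changes; the C-SSRS bullet speaks only of changes. Section 6.3 adds, for demographic and baseline data, that "Descriptive summaries of discrete data will include frequencies expressed in terms of number and percentage of patients", and Section 6.5 ties change-from-baseline statistics to continuous parameters. A shift table is therefore a fair reading, and in it the patient of step 2 would appear in the positive-to-positive cell. This stands: that new reports must average out is something a reader might infer, but the text does not establish it. What remains is that the bullet asks for no incidence, and that a shift by visit would still class that patient as unchanged.

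A reader might also infer that an event at Week 25 disappears once Week 53 is clear. The bullet says over time, so a summary by visit would show the Week 25 report. What such a summary lacks is the count of patients with any report.

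A third inference would be that suicidality goes unseen in this trial. The documents do not support that. Section 5.1 requires adverse events found by questioning or other means to be recorded, Section 6.4 tabulates adverse and serious adverse events, and Section 3.2.1 gives the iDMC regular review of them until the parent studies are unblinded. A certified rater conducts the C-SSRS interview, so a positive answer is known at the site. Section 4.1.2 also excludes patients judged at risk of suicide, which may lower the rates. Even so, adverse events are elicited by non-directive questions (Section 5.3.2), whereas the C-SSRS is the structured interview and deserves a summary that fits it.

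Finally, details could come in a later SAP. Sections 1.3.3, 6.5, 6.5.2 and 6.6 defer several matters to it, but none of them mentions the C-SSRS.

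**Conclusion.** The point holds as a minor defect of specification. The one planned C-SSRS analysis does not measure incidence, and the incidence summary given to comparable measures in the same list is missing. The patient-level result (no change despite a newly recorded instance) follows from the form and the bullet. The group-level cancellation is conditional on averaging, and its size (9 to 46 new reports per visit at 1% to 5%) rests on assumed rates and severity. The loss is confined to the structured C-SSRS result.

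Two things are not stated and are not relied on. The documents do not say which C-SSRS version the parent studies used at Week 105; if it was also a since-last-visit form, the baseline is simply one earlier window. Nor do they fix the length of each window: the last visit could mean the last C-SSRS assessment or the last dosing visit, and the form 4 weeks after the last dose may cover a short period. Change from baseline is not a count of new events under any of these.

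**What to change.** Replace the bullet in Section 6.4 and in the synopsis with wording such as:

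*Number and percentage of patients, by parent-study treatment group, with (a) any suicidal ideation, (b) any suicidal behaviour, and (c) treatment-emergent or worsening ideation or behaviour relative to the pre-OLE reference period, on any post-baseline OLE C-SSRS form; and a shift table of worst OLE category against worst category in the reference period.*

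Define the categories, and choose the reference period before the data are examined: the parent Week 105 report alone, or a longer part of the double-blind period. A longer period will class fewer OLE reports as new; items (a) and (b) do not depend on the choice. State whether the form 4 weeks after the last dose counts, and correct the abbreviation to C-SSRS.

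The cost is a few more tables and one definition. The data are already collected, and no visit, form or patient procedure changes.

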6.5 EFFICACY ANALYSES

All efficacy data during the open-label study will be summarized using descriptive statistics for the ITT population. Observed values and change from the OLE baseline values at each scheduled visit will be summarized.

For all continuous safety parameters, efficacy parameters, and biomarkers, *descriptive statistics for the change from baseline will be generated using the baseline value for the*

OLE study (defined as the last value recorded during the DBTP). *Descriptive statistics may also be generated for the change from the DBTP baseline.*

All efforts will be made to minimize missing data. Descriptive summaries of the number of patients with missing data and the timing and reasons for discontinuation from study will also be provided. Additional details will be documented in the SAP.

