In the Phase II studies ABE4869g and ABE4955g, serum crenezumab concentrations were measured in samples collected after biweekly SC (300 mg) or monthly IV (15 mg/kg) administration in patients with mild to moderate AD. In general, serum PK concentrations were similar between patients in the two Phase II studies. The higher dose of 15 mg/kg crenezumab administered Q4W by IV infusion resulted in approximately a 1.5-, 2.5-, and 5-fold higher exposure as measured by trough concentration, AUC, and peak concentration at steady-state, respectively, than the lower dose of 300 mg crenezumab administered Q2W by SC injection. For patients in the IV and SC treatment groups, steady-state trough serum crenezumab levels appeared to have been attained between Weeks 13 and 25 in both studies (after 3–6 IV doses or 6–12 SC doses, respectively). In Study ABE4869g, after 68 weeks of dosing with IV (Q4W) crenezumab, mean (SD) steady-state trough serum crenezumab levels were 118 (72) $\mu\text{g/mL}$, and steady-state peak serum crenezumab concentration levels were 447 (124) $\mu\text{g/mL}$. For comparison, the equivalent steady-state trough serum crenezumab levels for SC dosing were 69 (29.6) $\mu\text{g/mL}$. The trough crenezumab levels in CSF were measured in a subset of patients in Study ABE4869g and in all patients in Study ABE4955g. At Week 69, crenezumab penetration into the CSF was similar between the two studies as well as between the SC and IV doses, with a mean crenezumab CSF/serum ratio of approximately 0.3%. [REDACTED]

[REDACTED]

In the Phase Ib study (GN29632), a PK analysis based on data from the 13-week DBTP at doses of 30, 45, 60, and 120 mg/kg IV Q4W has been performed. Crenezumab pharmacokinetics increased proportionally at doses up to 120 mg/kg Q4W and was consistent with the PK findings in prior studies of crenezumab.

Additional PK information is provided in the Crenezumab Investigator's Brochure.

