1.3.3 Efficacy

An exploratory objective of this OLE study is to investigate the effect of crenezumab on the underlying disease process and course.

The purpose of Studies BN29552 and BN29553 is to establish the efficacy and safety of crenezumab in patients with pAD to mAD who may or may not be treated concurrently with approved symptomatic treatments for AD, over a treatment period of 104 weeks (26 doses). This DBTP was selected to demonstrate an enduring clinical benefit of crenezumab treatment on the basis of the mechanism of action and available data to date. Crenezumab may slow clinical decline rather than provide improvement over baseline.

There is considerable scientific and clinical interest in understanding the impact of the intervention under study on the underlying disease process. It has been proposed that demonstration of a disease-modifying effect (rather than a reversible "symptomatic" effect) may be achieved in studies using a two-period design (Leber 1997; see [Figure 1](#)).

Figure 1 Randomized Start Design

Therefore, an exploratory randomized start analysis is proposed, using the 2-year DBTP in Studies BN29552 and BN29553 as Period 1 (i.e., Treatment Initiation Group 1 in the

[figure not shown]
above diagram), and 1 or 2 year(s) of treatment in Study BN40031 as Period 2 (i.e., Treatment Initiation Group 2 in the above diagram). The intent is to demonstrate that patients who received placebo treatment in Period 1 will not achieve in the medium term the same clinical benefit as those patients who received active drug treatment in Period 1. Period 2 has to provide sufficient time for crenezumab to exert its effect on the patient group who previously received placebo. At the same time, it is important to keep the amount of missing data low to enable a robust analysis. The duration of Period 2 (1 or 2 years) is to be confirmed in the Statistical Analysis Plan (SAP).

The efficacy assessments in Study BN40031 will use the same scales as in the prior Phase III studies with the CDR-SB being the primary efficacy endpoint for this exploratory two-period design.

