1.3.4 Dose

Considering the evidence from the Phase II studies and clinical modeling, and based on supportive safety data from Study GN29632, the dose of 60 mg/kg IV Q4W was selected for the global Phase III program (60 mg/kg IV Q4W is a dose resulting in exposure approximately 4-fold higher than the high dose in the Phase II program, see [Figure 2](#)). A higher dose than that used in the Phase II program is expected to result in increased brain exposure and thus in increased target engagement and has the potential for better efficacy. This dose is currently used in Studies BN29552 and BN29553, and it is also the planned dose in this OLE.

Figure 2 Pharmacokinetic Profile Based on Modeling and Simulation Data for 60 mg/kg of Crenezumab Administered Intravenously Every 4 Weeks Compared with 15 mg/kg Crenezumab Administered Intravenously Every 4 Weeks

Conc = concentration; EC₅₀ = 50% effective concentration; Q4W = every 4 weeks;
 Note: Dashed red line = EC₅₀.

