3. STUDY DESIGN

3.1 DESCRIPTION OF THE STUDY

Study BN40031 is a Phase III, OLE, multicenter study to evaluate the long-term safety and tolerability of crenezumab at a dose of 60 mg/kg IV Q4W in patients with AD who have participated in one of the Phase III *parent studies* (BN29552 or BN29553). Efficacy will also be assessed. Patients who discontinued early from study treatment during Study BN29552 or BN29553 but remained in the study for safety and additional efficacy evaluations and completed the Week 105 study visit can enter the OLE study and begin open-label treatment. Patients from Study BN29552 or BN29553 who discontinued the study prior to completion of the Week 105 study visit are not eligible for this OLE study.

Studies BN29552 and BN29553 are ongoing Phase III, multicenter, randomized, double-blind, placebo-controlled, parallel-group, efficacy and safety studies of crenezumab in patients with pAD to mAD. The planned number of patients for this OLE study is not expected to exceed 1500 (approximately 750 randomized to crenezumab 60 mg/kg IV and 750 randomized to placebo, i.e., the total planned number of patients in the *parent studies* BN29552 and BN29553, not including patients from the China extension study). An estimate for the actual number of patients in this OLE study is approximately 925 patients (*not including patients from the China extension study*) based on 1500 patients enrolled in both Phase III studies and an estimated reduction by 35% (i.e., withdrawals from double-blind treatment) and by a further 5% of completers who may not opt to enroll in this OLE study. Approximately 350 centers in approximately 40 countries worldwide will participate in this study.

Patients and all clinical site staff will remain blinded to the original treatment assignment in Studies BN29552 and BN29553 on entry into the OLE study and until a later time which will be determined by the Sponsor.

Following completion of the global enrollment phase of Study BN29553, additional patients will continue to be enrolled in a China extension phase (i.e., China extension to the main Phase III study BN29553) to ensure a total enrollment sufficient to support registration in the People's Republic of China. This China subpopulation may include patients enrolled at sites in China during both the global enrollment phase and the China extension phase and could be included in this OLE, if applicable.

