3.2 STUDY DESIGN

All patients who are enrolled in the OLE study will receive crenezumab 60 mg/kg administered by IV infusion Q4W.

Data collected at Week 105 of the DBTP of Studies BN29552 and BN29553 and results from a coagulation blood test taken before the first OLE infusion will be used to assess patient eligibility for the OLE study. This Week 105 data will also be used as OLE baseline data.

Prior to administering the first infusion in the OLE, eligibility will be ensured by reviewing Week 105 assessment results (*including MRI results*), *OLE screening* coagulation blood test results, and any other significant patient changes.

Once a patient is identified as eligible for the OLE study, the following will occur:

- Patients can receive the first infusion of crenezumab at any time on or up to 8 weeks after the Week 105 visit of the double-blind studies. Any extensions to this period must be approved by the Sponsor. Sites can arrange an infusion visit as soon as *eligibility assessment results* are available (including MRI results and results from the coagulation test) to assess OLE eligibility. Details of the visit schedule and associated assessments are given in [Appendix 1](#).
- The day that the first dose of crenezumab is administered will be Visit 1, Week 1 of the OLE.
- On Visit 1, Week 1 of OLE (i.e., the first open-label infusion of crenezumab), safety assessments must be done as indicated in the schedule of activities (see [Appendix 1](#)).

For details on the schedule of activities, see [Appendix 1](#). For details on the length of the study, see Section [3.3](#).

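### Required mean-change safety tables start from an on-drug value in former-crenezumab patients who stayed on treatment, and timing of adverse events, part of the primary endpoint, has no analysis in Section 6.4

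*Combined protocol and SAP*

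**What the plan says.** **Reference value.** Section 6.5, although headed as efficacy, sets the rule for continuous safety parameters too: "descriptive statistics for the change from baseline will be generated using the baseline value for the" OLE, defined as the last double-blind value. Section 3.2 places this at the final parent-study visit: "This Week 105 data will also be used as OLE baseline data". The alternative is left open: "Descriptive statistics may also be generated for the change from the DBTP baseline". Section 6.4 asks for mean laboratory, ECG and vital-sign changes from baseline, and for treatment-emergent abnormal laboratory values, without saying which baseline is meant.

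**Timing.** Section 2 (Table 1) names timing, beside nature, frequency and severity, in the primary endpoint for adverse events (AEs) and serious adverse events (SAEs). Section 6.4 lists incidence, nature and severity for these, incidence for events of special interest, and incidence and nature for ARIA. It groups patients by the treatment they actually received before the OLE. The only Kaplan-Meier text is in Section 6.5.1, under exploratory efficacy, and it reports a median. Where Section 6.5 speaks of timing, it means study discontinuation.

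**The concern.** Long-term safety is the primary objective, and all its analyses are descriptive, so which tables are mandatory decides what the study will show.

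First, if a laboratory, vital-sign or ECG mean moved during two years of crenezumab and then held steady, the required table would show roughly no change in the longest-exposed patients. It would show whether the Week 105 level is held, but not how far that level lies from the pre-drug one.

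Second, a crude percentage over unequal follow-up cannot show whether events cluster after first exposure or accumulate. The protocol gives reason to ask: Section 1.2.3.3 places all serious Phase II pneumonia cases 7 to 13 months after the first dose, and Section 5.1.3.2 says that ARIA with other antibodies tends to come early.

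**Working it through.** **Part 1: is Week 105 an on-drug value?**

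- Section 1.3.3 gives 26 doses over 104 weeks. Every 4 weeks from Week 1, the last falls at Week 1 + 25 × 4 = Week 101, 28 days before Week 105. The parent schedule is not supplied, so this is inferred.
- Section 1.2.5 says of the Phase II studies that "steady-state trough serum crenezumab levels appeared to have been attained between Weeks 13 and 25". Week 105 is well past that.
- Phase II steady-state trough over peak (Section 1.2.5): 118/447 = 0.26. As a cross-check, half-lives of 17 and 26 days leave 0.5^(28/17) = 32% and 0.5^(28/26) = 47% of the last dose's concentration, on a single-exponential approximation.
- Section 1.3.4 describes the present dose as giving "exposure approximately 4-fold higher than the high dose in the Phase II program". With dose proportionality, the trough is about 4 × 118 = 472 µg/mL. This shows exposure, not harm.

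| Group | Week 105 value | What change from Week 105 shows |
|---|---|---|
| Former placebo | Before any crenezumab | On-drug change from a pre-drug value |
| Former crenezumab, stayed on treatment | Steady-state trough | Change during the OLE only |
| Former crenezumab, stopped early | May be off drug | Mixed |

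The third row exists because Section 3.1 admits "Patients who discontinued early from study treatment during Study BN29552 or BN29553 but remained in the study" through Week 105. The documents give no size for any laboratory, vital-sign or ECG shift, so none is computed.

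**Part 2: what does crude incidence leave out?**

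The plan's own entry figure first: 1500 × 0.65 × 0.95 = 926, against about 925 stated in Section 6.1. Half, 463, are taken as former placebo.

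*Clustering.* Phase II serious pneumonia risk is 6/349 = 1.7% (Sections 1.2.3 and 1.2.3.3). Expected cases: 463 × 6/349 = 8.0. Cumulative hazard: H = −ln(1 − 6/349) = 0.0173. Suppose it accrues over 24 months without dropout, either wholly within months 7 to 13 (A) or at the constant rate H/2 = 0.0087 per year (B).

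| | A: cluster | B: constant |
|---|---|---|
| Incidence at 24 months | 1.7% | 1.7% |
| Overall rate per 100 patient-years | 0.87 | 0.87 |
| Cases in months 0–7 / 7–13 / 13–24 | 0 / 8 / 0 | 2.3 / 2.0 / 3.6 |
| Rate per 100 patient-years in months 7–13 | H/0.5 = 3.5 | 0.87 |
| Cumulative incidence at 7 / 13 / 24 months | 0 / 1.7 / 1.7% | 0.5 / 0.9 / 1.7% |

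Neither crude incidence nor one overall rate separates the two; the last three rows do. A Kaplan-Meier median would not be reached at such incidences.

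*Unequal follow-up.* Section 3.3 gives about 4 years in all, ending about 28 months after the last enrolment. Entry therefore spans about 48 − 28 = 20 months, and OLE time runs from about 24 to 44 months (Section 3.3 rounds the longest to about 4 years). Take all Phase II pneumonia in crenezumab patients, 11/349 over 72 weeks: h = −ln(1 − 11/349)/(72/52) = 0.0231 per year. With k = −ln(1 − annual dropout), crude incidence is the mean of h/(h + k) × [1 − exp(−(h + k)t)] for t uniform on 2 to 3.67 years.

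| Annual dropout | 0% | 10% | 20% | 30% |
|---|---|---|---|---|
| 72-week denominator | 6.3% | 5.5% | 4.7% | 4.0% |
| 84-week denominator | 5.5% | 4.7% | 4.0% | 3.4% |

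Within each row the underlying hazard is the same throughout.

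**The case against.** *No shift is in evidence.* Section 1.2.3 reports no population trend in laboratory, vital-sign or ECG parameters. A reader might infer that the baseline rule hides a known effect; the documents do not support that.

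*The parent trials answer the earlier question, with a placebo arm.* The OLE looks beyond the first two years (Section 1.3.2), and change from Week 105 fits that purpose. This stands as a reason to keep the OLE-baseline table, but not to leave the other optional for the longest-exposed group.

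*The former-placebo group already supplies on-drug change from a pre-drug value, and incidences of abnormal ECG and vital-sign findings are not expressed as change from baseline.* Both are true, and they confine the point to the mean-change tables of one group.

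*A simple onset summary would meet the timing endpoint, and the contrast above is extreme.* Partly right. With 463 × 0.5 = 231.5 patient-years in the window, exact 95% intervals are about 1.5 to 6.8 per 100 patient-years for 8 cases and 0.1 to 3.1 for 2 cases; they overlap. The table shows what each summary can reveal, not what this study would prove.

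*Kaplan-Meier suits some events badly.* This stands. ARIA is found mainly at scheduled MRI (Section 5.1.1), so its curve would largely follow the scan calendar. Death is also a competing event: 4.2% died in the Phase II OLE (Section 1.2.3.2).

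A reader might also infer that staggered entry biases the comparison of the former arms. The documents do not show this: safety is grouped by prior treatment, and nothing says that entry dates differ between the groups.

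**Conclusion.** Both parts hold within limits. The required mean-change tables cannot show a shift acquired on drug before Week 105 in former-crenezumab patients who stayed on treatment. A named component of the primary safety endpoint has no analysis in Section 6.4, although planned treatment differs between patients by up to about two years.

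It would go too far to say that the plan nowhere analyses the timing of adverse events. Section 6.5 refers further detail to a separate SAP whose text is not supplied, and it may contain such an analysis.

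No test, sample size or data collection is affected. The size of any baseline shift is unknown. The pneumonia figures are illustrations. They assume that Phase II risk carries over, that half of entrants are former placebo, that entry is even, that hazards follow the stated patterns, and that annual dropout is 0 to 30%, for which the documents give no figure. Confidence is medium. The changes should be made as a cheap improvement.

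**What to change.** **Section 6.5.** For laboratory, vital-sign and ECG parameters, change *may* to *will* for change from the double-blind baseline. Show it for both prior-treatment groups beside the OLE-baseline change. Using the same two references in both groups keeps elapsed time equal. For former-placebo patients the OLE baseline already serves as the pre-drug reference, so no third one is needed. State which reference defines treatment-emergent laboratory values.

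**Section 6.4.** Beside incidence, by prior-treatment group, add:

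- for AEs, SAEs and events of special interest, rates per 100 patient-years with 95% confidence intervals, overall and by period since the first crenezumab dose;
- for first SAE and first pneumonia, cumulative incidence at fixed times with death as a competing event. For former-crenezumab patients, use delayed entry at OLE start, because those who stopped permanently for safety reasons are excluded (Section 4.1.2);
- for ARIA, incidence by scheduled MRI interval (Weeks 13, 25, 53, 105, then yearly) among patients scanned, instead of Kaplan-Meier.

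**Cost.** No new data are needed: event dates are recorded (Section 5.1) and parent-study baselines exist. The costs are extra tables and a merge of parent-study safety data with the OLE. Change from the double-blind baseline in an uncontrolled period also reflects ageing and disease progression, and the tables should say so.
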